#### **7.5.3.2 HBV DNA Reduction from Baseline**

HBV DNA values and changes from baseline ( $\log_{10}$  IU/mL) are summarized by treatment regimen at baseline and each scheduled visit on treatment through Week 48.

The difference (ETV - PBO) and 95% CI at Week 48 are also presented. The difference and CI are estimated from a linear regression model of Week 48 HBV DNA change from baseline on covariates baseline HBV DNA, treatment regimen and age randomization strata.

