## 2 STUDY DESCRIPTION

### 2.1 Study Design

This is a comparative, randomized, double-blinded, placebo-control, multicenter study, assessing the efficacy and safety of ETV in pediatric subjects with chronic HBV infection who are HBeAg-positive and nucleos[t]ide naive (< 12 weeks of prior therapy with any nucleos[t]ide antiviral agent with activity against hepatitis B virus). Chronic HBV-infected children and adolescents from 2 to < 18 years of age will be enrolled. Approximately 180 subjects will be randomized 2:1 to ETV or placebo (PBO) for a maximum of 96 weeks of blinded therapy, with the primary endpoint at Week 48 for the first 123 randomized subjects (the Primary Cohort). The randomization will be stratified by age group ( $\geq 2$  to  $\leq 6$ ,  $> 6$  to  $\leq 12$ ,  $> 12$  to  $< 18$  years). To ensure adequate representation, the target enrollment will be 30 subjects for each age group, with a minimum requirement of 18 subjects. At Week 52, an assessment of HBeAg seroconversion shall be performed based on Week 48 serology results. At the Week 52 assessment, all subjects who achieve HBeAg seroconversion will remain on blinded therapy through Week 96; subjects without HBeAg seroconversion will be switched to open-label ETV. Thereafter, assessment of HBeAg seroconversion shall be conducted at study Weeks 100 and 148 during the open label treatment. Study subjects who achieve HBeAg seroconversion during open label ETV at the respective assessment time points shall receive up to an additional 48 weeks of study treatment for consolidation (extended treatment to strengthen study drug effects). Open-label ETV may therefore be continued up to Week 144 in ETV randomized subjects and Week 192 for placebo randomized subjects. All randomized study subjects who do not achieve HBeAg seroconversion will receive a maximum of 96 weeks of study ETV therapy.

After completing the blinded treatment or the open-label phase, all subjects will be followed in an observational long-term follow up phase until they complete a total of 5 years of study participation from the start of blinded treatment.

The total duration of the study will be 264 weeks (5 years); the end of the study is defined as the date of the last follow-up visit. Study visits will occur at screening, Baseline, Weeks 4, 8, 12, and

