### 5 SAMPLE SIZE AND POWER

One hundred and twenty-three (123) subjects (randomized 2:1 to ETV vs placebo) in this study provide 90% power to show superiority of ETV versus PBO assuming a response rate for the primary endpoint HBV DNA by PCR < 50 IU/mL (approximately 300 copies/mL) and HBeAg seroconversion of 20% for ETV and 1% for PBO. A two-sided significance level of 0.05 is used. Subjects who either discontinue from study treatment prior to Week 48 or have having missing Week 48 HBV DNA or HBeAg serology measurement are considered as failures at Week 48 (Non-Completer = Failure). The efficacy estimate for ETV is derived from an analysis of the identical endpoint (HBV DNA by PCR < 300 copies/mL and HBeAg seroconversion) in the pivotal Phase 3 study of HBeAg-positive subjects, (AI463022). The efficacy estimate for PBO is derived from evidence in the literature which shows that whereas spontaneous seroconversion occurs at a relatively high rate in children, viral replication remains detectable using sensitive PCR assays. The results of the Gilead Sciences' pediatric CHB study (GS 518) support this estimate; 3 of 57 placebo treated subjects (5.3%) achieved HBeAg seroconversion, but only 1 of 58 subjects (1.7%) achieved HBV DNA < 2.23 log10 copies/mL at Week 48.

This sample size also fulfills the requirement that the ETV integrated pediatric safety database has at least 100 pediatric subjects who have received ETV for at least 48 weeks; this database will be comprised of subjects currently enrolled in study AI463-028 and from this study (AI463-189).

Currently 24 nucleoside naive subjects are enrolled in AI463-028; all 24 would have had 48 weeks of safety data collection by the time study AI463-189 reaches Week 48.

Based on the original planning for study AI463-189, it is estimated that 175 subjects will be enrolled to have approximately 123 subjects randomized (approximately 30% screen failure rate). Randomization is 2:1 (ETV 82: PBO 41); assuming a 10% drop out rate per year and even enrollment for 2 calendar years, approximately 72 ETV randomized subjects will have 48 weeks of safety data by study Week 144. This brings the number of subjects that will be included in the integrated safety database at the end of study Week 144 to approximately 96 subjects.

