## 8.6 HBV DNA Below LOQ or LLD

HBV DNA < LOQ is identified by the specify field “DETECTED BUT BELOW LOQ” or NOT DETECTED”.

HBV DNA < LLD is identified by the specify field “NOT DETECTED”.

In analyses of HBV DNA as a continuous variable, HBV DNA < LOQ or LLD is assigned a value 1 IU less than the LOQ i.e., 28 IU/mL.

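### SAP 7.5.3.2 names no variance method for the Week 48 HBV DNA change CI, so under 2:1 allocation and the 28 IU/mL floor its 95% coverage is not assured (minor)

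*SAP*

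**What the plan says.** SAP 7.5.3.2 presents the ETV minus placebo difference in Week 48 change with a 95% CI: "The difference and CI are estimated from a linear regression model of Week 48 HBV DNA change from baseline". The covariates are baseline HBV DNA, treatment regimen and age strata. No treatment-by-baseline term is listed, no variance estimator is named, and no p-value is planned.

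SAP 8.6 governs the outcome variable. When HBV DNA is analysed as continuous, a result below LOQ or LLD "is assigned a value 1 IU less than the LOQ", that is 28 IU/mL.

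On allocation, SAP 5 gives "Randomization is 2:1 (ETV 82: PBO 41", and SAP 2.1 gives the enlarged study: "Approximately 180 subjects will be randomized 2:1 to ETV or placebo (PBO".

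For the binary endpoints, SAP 7.5 does state a variance method: the standard error of a difference in proportions uses unpooled, arm-specific proportions. SAP 7.5.3.2 has no counterpart.

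**The concern.** An ordinary regression CI pools the residual variance over both arms. With equal arms, pooling does little harm even if the spreads differ. At 2:1 the pooled figure is dominated by the larger arm, while the true variance of the difference is dominated by the smaller one, so unequal spread passes straight into the width of the CI.

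The LOQ rule makes unequal spread likely. A floored subject has change equal to log10(28) minus baseline exactly: slope -1 and no scatter. Far more ETV than placebo subjects should reach the floor. This is the only between-arm estimate that the SAP specifies on the log10 scale, and readers will take its 95% label at face value. What is at stake is reported precision.

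**Working it through.** **1. The plan's own figure.** The documents give no power, SD or CI width for this analysis. The figure that can be checked is the sample size: "A two-sided significance level of 0.05 is used"; 123 subjects "provide 90% power to show superiority of ETV versus PBO", assuming "HBeAg seroconversion of 20% for ETV and 1% for PBO" (with HBV DNA < 50 IU/mL as the other component). With pooled variance, no continuity correction and a 2:1 ratio, the pooled rate is (0.01 + 2 × 0.20)/3 = 0.1367 and

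n(placebo) = [1.960 × √(0.1367 × 0.8633 × 1.5) + 1.282 × √(0.01 × 0.99 + 0.20 × 0.80/2)]² / 0.19² = (0.8245 + 0.3843)²/0.0361 = 40.5, rounded up to 41.

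The total is 3 × 41 = 123, with power 0.904. The stated figure reproduces.

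**2. Numbers with Week 48 data.** The plan's dropout figure ("assuming a 10% drop out rate per year") gives 0.9 × 82 ≈ 74 and 0.9 × 41 ≈ 37. For the enlarged study, 120:60 becomes 108:54.

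**3. The floor.** log10(28) = 1.447. For placebo, Protocol 8.1 cites 1 of 58 subjects (1.7%) below 2.23 log10 copies/mL. That is 169.8 copies/mL, and 169.8/5.82 = 29.2 IU/mL, essentially the LOQ. For ETV, the planned composite rate implies at least 20% below 50 IU/mL. The share below LOQ is not given, so 20% to 70% is assumed.

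**4. Closed form, ignoring slopes.** Let sE and sP be the residual SDs and n the placebo size, with 2n on ETV.

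- Model-based variance: [(2sE² + sP²)/3] × [3/(2n)] = (2sE² + sP²)/(2n)
- True variance: sE²/(2n) + sP²/n = (sE² + 2sP²)/(2n)
- SE ratio k = √[(2sE² + sP²)/(sE² + 2sP²)]; coverage = 2Φ(1.96k) − 1

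Example: at sE/sP = 0.5, k = √(1.5/2.25) = 0.816 and coverage is 89.0%.

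| sE/sP | k | Coverage |
|---|---|---|
| 0.5 | 0.82 | 89.0% |
| 0.67 | 0.88 | 91.6% |
| 1 | 1.00 | 95.0% |
| 1.5 | 1.14 | 97.4% |
| 2 | 1.22 | 98.4% |

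The limits are k = √½ = 0.71 (83.4%) and √2 = 1.41 (99.4%). At 1:1 the two variances are identical and k = 1.

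**5. Simulation with the SAP's floor.** Week 48 change was regressed on treatment, baseline and three age strata, with values below 29 IU/mL set to 28. Assumptions: baseline centred on 8 log10 IU/mL (the SAP's subgroup cut) with SD 1; SDs of change as shown; about 1.7% of placebo subjects floored. Sizes are 74:37. Residual SDs are those of the simulated data; the last three columns are model-based, then HC3.

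| ETV floored | SD of change, ETV/placebo | Residual SD, ETV/placebo | k from step 4 | Simulated SE ratio | Coverage | CI width, log10 |
|---|---|---|---|---|---|---|
| 20% | 2 / 0.5 | 1.68 / 0.95 | 1.19 | 1.19 | 98.1%; HC3 95.5% | 1.19; HC3 1.02 |
| 20% | 1.5 / 1 | 1.28 / 1.28 | 1.00 | 0.99 | 94.8%; HC3 95.0% | 1.02; HC3 1.05 |
| 50% | 1.5 / 1 | 0.92 / 1.29 | 0.90 | 0.88 | 91.6%; HC3 94.7% | 0.86; HC3 0.98 |
| 70% | 1.5 / 1 | 0.67 / 1.28 | 0.82 | 0.83 | 89.5%; HC3 95.3% | 0.77; HC3 0.95 |
| 70% | 1 / 2 | 0.48 / 2.14 | 0.73 | 0.73 | 85.0%; HC3 95.2% | 1.06; HC3 1.47 |

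The closed form predicts the simulated SE ratios closely, so residual variance explains most of the error.

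**6. Wider grid.** Over 72 scenarios at 74:37 (floor 20% to 70%, ETV SD 1 to 2, placebo SD 0.5 to 2, baseline SD 0.8 to 1.2), model-based coverage ran from 84.3% to 98.5%. HC3 coverage ran from about 90.6% to 95.7%, lowest where a few floored placebo subjects dominate a small placebo variance. Monte Carlo error is about 0.3 to 0.7 points.

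**7. Separating the causes.** With equal residual SDs, slopes of -1 and 0 gave 93.2% to 93.8%; gaps of 0.7 or less gave 94.2% to 95.1%. The five scenarios above, rerun at about 1:1 (55:56), gave 94.2% to 95.1%. At 108:54 they still ranged from 85.5% to 98.1%, so more subjects do not cure the problem.

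**The case against.** The strongest case against rests on four arguments, all of which limit the point.

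- **No SDs are given.** A reader might infer that the CI has the wrong width. The documents do not support that: it may be too narrow, too wide or about right, as the 94.8% row shows.
- **The floor does not by itself prove unequal variance.** Zero scatter applies only to floored subjects, and the ETV arm mixes floored and unfloored ones. Raising the floored share shrinks the ETV residual SD, which can bring the arms together before it drives them apart. Unequal spread is likely but not established.
- **Equal variance is read from silence.** A linear regression with no stated variance method would normally be run with the model-based SE, but the SAP does not write this down.
- **The consequence is small.** A reader might take this as the only between-arm virologic effect size. It is not: HBV DNA < 50 IU/mL and < LOQ are compared between arms as key secondary endpoints (SAP 7.5.2.1 and 7.5.2.3), with the unpooled standard errors of SAP 7.5. The analysis here is listed under other Year 1 efficacy and carries no p-value. Simulated differences of -3.9 to -5.9 log10 far exceed CI widths of 0.5 to 1.5.

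It is also fair that HC3 changes only the interval. The point estimate still depends on substituting 28 IU/mL.

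What survives is narrow: the plan commits to a 95% CI and leaves open a choice that decides whether it behaves as one.

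**Conclusion.** The point holds as a minor one. The default CI is not assured of 95% coverage: about 84% to 98.5% over the assumed grid, with the direction unknown in advance. The firm parts are the 2:1 allocation, the main-effects model, the absence of a stated variance method and the 28 IU/mL rule. The SDs, the ETV floor shares and the baseline distribution are assumptions. The common slope is secondary, worth at most 95.0 − 93.2 = 1.8 points in the cases tried. No superiority conclusion and no step in the testing sequence depends on this CI.

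**What to change.** Add one sentence to SAP 7.5.3.2: the model and point estimate stay as specified, and the 95% CI uses a heteroscedasticity-consistent (HC3) standard error or a residual variance estimated separately by arm. This brings the continuous endpoint into line with the unpooled standard errors that SAP 7.5 already uses for proportions. A treatment-by-centred-baseline term is optional.

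The cost is that sentence and one procedure option. It needs no further data, subjects or alpha. The CI may become wider or narrower than the default; in the tabulated scenarios its width changed by between −0.17 (1.19 to 1.02) and +0.41 log10 (1.06 to 1.47).

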### **7.5.4 Year 2 Efficacy**

The following binary endpoints are summarized by treatment regimen with response rates using NC = F and NC = M at baseline and each scheduled visit on treatment through Week 96 for the Year 2 Efficacy Cohort (see [Section 6.3](#)):

- HBV DNA < 50 IU/mL
- HBV DNA < 50 IU/mL and HBeAg seroconversion
- HBV DNA < 50 IU/mL and ALT normalization

- HBV DNA < LOQ
- HBV DNA < LLD
- HBV DNA < LOQ, LOQ - < 50, 50 - < 172, 172 - < 1,720, 1,720 - < 17,200 and  $\geq 17,200$  IU/mL
- ALT normalization
- HBeAg loss
- HBeAg seroconversion
- HBsAg loss
- HBsAg seroconversion

The Year 2 Efficacy Cohort is defined by as-randomized treatment regimen for all treated subjects and observed (NC = M) Week 48 HBeAg seroconversion status. Therefore, the analysis of HBeAg seroconversion addresses maintenance of HBeAg seroconversion at Week 96 for those who seroconverted at Week 48. Endpoints are summarized for PBO only through Week 48.

Key binary endpoints (e.g., HBV DNA < 50 IU/mL, ALT normalization, HBeAg seroconversion) at Week 96 are summarized by subgroups defined in [Section 7.5.1](#) using NC = F and NC = M for ETV subjects.

HBV DNA values and changes from baseline ( $\log_{10}$  IU/mL) are summarized by treatment regimen at baseline and each scheduled visit on treatment through Week 96 for the Year 2 Efficacy Cohort.

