4.1.1 Subject Management Decisions

Assessment of HBeAg seroconversion will be done, as needed, at Study Weeks:

- 52 (based upon Week 48 result);
- 100 (based upon Week 96 result); and
- 148 (based upon Week 144 result).

The investigators shall conduct the assessment of HBeAg response status at the assessment time points; this will be cross checked centrally by the BMS Medical Monitor/Protocol Manager. Subjects achieving HBeAg seroconversion shall initiate consolidation therapy for an additional 48 weeks as follows:

- At Week 52 (consolidation using blinded therapy to Week 96; 48 weeks counting from Week 48)
- At Week 100 (consolidation using open-label ETV to Week 144; 48 weeks counting from Week 96)
- At Week 148 (consolidation using open-label ETV to Week 192; 48 weeks counting from Week 144)

Subjects who achieve HBeAg seroconversion and revert back to HBeAg-positivity or develop HBeAg-negative CHB shall be managed as follows:

- Any subject who achieves HBeAg seroconversion by the Week 48 assessment and reverts to HBeAg-positive status before reaching Week 96 will be treated with open-label ETV until study Week 144, and then will stop study therapy and proceed to the LTFU phase;
- Any subject who achieves HBeAg seroconversion after the Week 48 assessment, who reverts back to HBeAg-positive status shall stop study treatment, if applicable, and be treated at the discretion of the investigator in consultation with the BMS Medical Monitor.
- Subjects who develop HBeAg-negative CHB (absence of HBeAg, presence of anti-HBe antibodies, active viral replication [HBV DNA by PCR assay $\geq 10,000$ copies/mL] and biochemical or histological evidence of hepatitis) shall be managed at the discretion of the investigator in consultation with the BMS Medical Monitor.

Study treatment (ETV and placebo) shall be provided during the blinded and open-label study treatment phases. Rescue open-label ETV shall be provided to subjects who experience extreme elevations of ALT due to acute exacerbations of CHB upon investigator request and approval by the Central Medical Monitor (see section 4.1.2).

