## 4.3 Other Secondary Endpoints

- The number and percent of subjects with adverse events (including palatability issues), serious adverse events (SAEs), discontinuations due to adverse events, and HBV disease progression through Week 48;
- Proportions of subjects with HBeAg loss at Weeks 48 and 96;
- Proportion of subjects with HBeAg seroconversion at Week 96;
- Proportion of subjects who maintained HBeAg seroconversion at Week 96 (end of blinded therapy) among subjects who achieved HBeAg seroconversion at Week 48;
- Histological analysis among subjects with available liver biopsy.

[REDACTED]

- [REDACTED]

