## 6 STUDY PERIODS, TREATMENT REGIMENS AND POPULATIONS FOR ANALYSES

### 6.1 Study Periods

Study periods for efficacy and safety analyses are defined as follows:

- **Pre-treatment period** begins at the first visit until initiation of study therapy.
- **On-treatment period** begins after the first day of study therapy and ends at the last dose of study therapy plus 5 days.
- **ETV treatment period** begins after the first day of active ETV and ends at the last dose of active ETV plus 5 days.
- **Off-treatment follow-up period** begins on the last dose of study therapy plus 6 days and ends at the start of alternative anti-HBV therapy minus 1 day.
- **Long-term follow-up period** begins on the last dose of study therapy plus 6 days until the end of the study.
- **Alternative ETV follow-up period** begins on the later of the last dose of study therapy plus 6 days and the start of alternative ETV therapy, until the end of the study.

Note that rescue open-label ETV is considered alternative anti-HBV therapy. See [Section 8.9](#) for additional conventions.

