- **Year 2 Efficacy Cohort** is treated subjects grouped as-randomized and according to observed Week 48 seroconversion status: ETV, PBO, ETV S48, PBO S48, ETV NS48 and PBO NS48 (S = seroconverter; NS = non-seroconverter). All treated subjects are included in ETV and PBO.
  - **Year 2 Primary Efficacy Cohort** is treated subjects in both Primary and Year 2 Efficacy Cohorts.
- **Year 3 Efficacy Cohort** is observed Week 48 non-seroconverters grouped as-randomized according to observed Week 96 seroconversion status: ETV S96, ETV NS96, PBO S96 and PBO NS96.
- **Year 4 Efficacy Cohort** is PBO-randomized observed non-seroconverters at both Weeks 48 and 96 who seroconverted at Week 144.
- **All ETV Efficacy Cohort** is treated as-randomized ETV subjects and PBO-randomized subjects who received open-label ETV.
- **Post-Year 1 Efficacy Cohort** is treated subjects grouped as-randomized: ETV, PBO, PBO subjects who only received blinded PBO (PBO BL), PBO subjects who received open-label ETV (PBO OL), and All ETV (ETV and PBO OL combined; see previous bullet).
- **Year 2 Safety Cohort** is treated subjects grouped as-treated: ETV, PBO subjects who only received blinded PBO (PBO BL), and PBO subjects who received open-label ETV (PBO OL). In addition, subjects must have received open-label ETV or > 54 weeks of study therapy (the upper bound of the Week 48 visit window; see [Sections 7.4.1](#) and [8.4](#)).
- **All ETV Safety Cohort** is as-treated ETV subjects and as-treated PBO subjects who received open-label ETV.
- **Post-Year 1 Safety Cohort** is treated subjects grouped as-treated: ETV, PBO, PBO subjects who only received blinded PBO (PBO BL), PBO subjects who received open-label ETV (PBO OL), and All ETV (ETV and PBO OL combined; see previous bullet).

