## 8.9 Derived Dates

Derived dates that are used commonly in analyses are defined as follows. Derivations of dose dates exclude rescue open-label ETV.

- First dose date of study therapy is the earliest start date of drug (ie, blinded therapy [ETV active or PBO] or open-label ETV) identified from valid dosing records, ie, non-missing start date and number of units per day > 0, from blinded therapy study medication CRFs. This date is used to identify treated subjects and to distinguish measurements across study periods. Note that this is also first dose date of blinded study therapy.

- Dose end date of study therapy is the latest start or end dates of drug (ie, blinded therapy [ETV active or PBO] or open-label ETV) identified from valid dosing records, ie, non-missing start or end date and number of units per day > 0 or total dose > 0. This date is used to assess time on study therapy.
- Last dose date of study therapy is the dose end date of study therapy derived only for subjects with an end of treatment subject status CRF indicating whether the subject completed the treatment period. This date is used to exclude data in antiviral activity and safety analyses, and to distinguish measurements across study periods.
- Dose end date of blinded therapy is the latest start or end date of blinded therapy (ETV active or PBO) identified from valid dosing records, ie, non-missing start or end date and number of units per day > 0, from blinded therapy study medication CRFs. This date is used to assess time on blinded study therapy.
- First dose date of open-label ETV is the earliest start date of open-label ETV identified from valid dosing records, ie, non-missing start date and total dose > 0, from open-label study medication CRFs. This date is used to distinguish measurements across blinded vs open-label treatment, and to assess time on open-label therapy.
- Dose end date of open-label ETV is the latest start or end date of open-label ETV identified from valid dosing records, ie, non-missing start or end date and total dose > 0, from open-label study medication CRFs. This date is used to assess time on open-label therapy.
- First dose date of active ETV is the first dose date of study therapy for ETV-randomized subjects, and the first dose date of open-label ETV for PBO-randomized subjects. This date is used to identify all ETV-treated subjects and to distinguish measurements across study periods.

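### The Week 96 maintained-seroconversion endpoint scores Week 96 status alone, so a child who reverts, moves to open-label ETV and seroconverts again counts as maintained, and in PBO S48 does so under the placebo label

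*SAP*

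**What the plan says.** SAP 4.3 lists among the other secondary endpoints: "Proportion of subjects who maintained HBeAg seroconversion at Week 96 (end of blinded therapy) among subjects who achieved HBeAg seroconversion at Week 48". Protocol 8.3 has the same endpoint.

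SAP 6.3 builds the Year 2 Efficacy Cohort, which "is treated subjects grouped as-randomized and according to observed Week 48 seroconversion status". This gives ETV S48 and PBO S48 for the Week 48 seroconverters. SAP 7.5.4 presents visit-by-visit response rates through Week 96 in these groups and states that "the analysis of HBeAg seroconversion addresses maintenance of HBeAg seroconversion at Week 96 for those who seroconverted at Week 48".

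Protocol 4.1.1 provides that a Week 48 seroconverter who "reverts to HBeAg-positive status before reaching Week 96 will be treated with open-label ETV until study Week 144". The rule makes no distinction by randomised arm.

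The SAP's time definitions run through that switch. The on-treatment period in SAP 6.1 "begins after the first day of study therapy and ends at the last dose of study therapy plus 5 days". SAP 8.9 defines the drug behind those dates as "ie, blinded therapy [ETV active or PBO] or open-label ETV". Only rescue open-label ETV is left out of the dose-date derivations.

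**The concern.** The endpoint's name and its parenthesis describe a response held until blinded therapy ends. The calculation uses one visit. For a child who reverts and is switched, Week 96 is not the end of blinded therapy, and a seroconversion seen then may be a second one.

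The two arms are affected differently:

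- **PBO S48.** The child is on ETV at Week 96 but is reported under placebo. A loss of spontaneous seroconversion can be hidden by a later response on active drug. Even without a second seroconversion, post-switch HBV DNA and ALT enter the PBO S48 column as on-ETV values.
- **ETV S48.** The child goes from blinded to open-label ETV, so the drug does not change. The only fault is that one time point stands in for continuous maintenance.

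At stake is how the PBO S48 column reads beside ETV S48. The group is so small that a single child changes the picture.

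**Working it through.** **Plan's own figure.** The only stated sample size is 123 (82:41), for the primary endpoint at 20% against 1%, two-sided 0.05, 90% power. With the pooled-variance formula and allocation k = 2:

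- mean rate = (0.01 + 2 × 0.20)/3 = 0.1367
- placebo n = [1.960 × √(0.1367 × 0.8633 × 1.5) + 1.2816 × √(0.01 × 0.99 + 0.20 × 0.80/2)]² / 0.19² = (0.8245 + 0.3843)²/0.0361 = 40.5, so 41
- 41 + 82 = 123

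It reproduces and is unaffected by this point. No size or power is stated for the maintenance endpoint.

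**Following one child through the rules.** Take a PBO S48 child first seen HBeAg-positive at Week 60 and seroconverted at Week 96.

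1. SAP 6.3 fixes the group by randomised arm and Week 48 status: PBO S48.
2. Protocol 4.1.1 starts open-label ETV.
3. SAP 6.1 and 8.9 count open-label ETV as study therapy, so Week 96 is an on-treatment value.
4. SAP 7.5 (NC = F) fails a child for missing data at the analysis week, not for an earlier reversion or a switch.
5. SAP 7.5.4 takes the Week 96 status: maintained.

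Protocol Table 6.1 collects on-treatment serology every 12 weeks, so Weeks 60, 72 and 84 are observed. A reversion first seen at Week 60 leaves up to about 36 weeks on ETV before Week 96; one seen at Week 84 leaves up to about 12. The protocol does not say how quickly the switch follows.

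**Size of PBO S48.** Inputs are 60 placebo children (Protocol synopsis) and a Week 48 seroconversion rate of 5.3% (the placebo result of the cited pediatric study) to 10% (planning value), both in Protocol 8.1 and SAP 5.

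| Placebo n | Rate | Expected PBO S48 | One child moves the rate by |
|---|---|---|---|
| 60 | 5.3% | 60 × 0.053 = 3.2 | 100/3.18 = 31 points |
| 60 | 10% | 60 × 0.10 = 6.0 | 100/6.0 = 17 points |
| 41 | 5.3% | 41 × 0.053 = 2.2 | 100/2.17 = 46 points |
| 41 | 10% | 41 × 0.10 = 4.1 | 100/4.1 = 24 points |

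The rows for 41 matter because SAP 9 first presents Week 96 efficacy for the Year 2 Primary Efficacy Cohort. Dropout is ignored here. Applying the plan's 10% to the 60 gives 60 × 0.9 × 0.053 = 2.9 to 60 × 0.9 × 0.10 = 5.4 children, and 35 to 19 points.

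**ETV S48.** If the 20% composite rate holds, the group has at least 82 × 0.20 = 16.4 or 120 × 0.20 = 24 children. One child then moves the rate by at most 100/16.4 = 6 points or 100/24 = 4 points.

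**Distortion of the maintained rate.** Let r be the share reverting before Week 96 and q the share of those seroconverted again at Week 96. Then the apparent rate is (1 − r) + r × q, against a continuous rate of 1 − r; the excess is r × q. The documents give neither r nor q, so these are assumed ranges:

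| r | Continuous | q = 0 | q = 10% | q = 50% |
|---|---|---|---|---|
| 10% | 90% | 90% | 91% | 95% |
| 25% | 75% | 75% | 77.5% | 87.5% |
| 50% | 50% | 50% | 55% | 75% |

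The expected number of such placebo children is group size × r × q. Over the non-zero values it runs from 3.18 × 0.1 × 0.1 = 0.03 to 6 × 0.5 × 0.5 = 1.5; at q = 0 it is zero.

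**The case against.** The strongest counter-argument is the sentence in SAP 7.5.4 that ends the PBO summary at Week 48. If it covers every placebo group, PBO S48 has no Week 96 result and the placebo part of the point falls. That reading is possible but less likely:

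- SAP 6.3 lists PBO, holding all treated placebo children, as a group separate from PBO S48.
- SAP 7.5.5 names the subgroup when it truncates one.
- SAP 7.5.2.5 still compares ETV S48 with PBO S48 after treatment.
- Stopping PBO S48 at Week 48 would leave the SAP 4.3 endpoint with no placebo result.

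The text remains ambiguous, and the ETV S48 part stands either way.

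It can also be said that status at Week 96 by randomised arm is a conventional summary, that rates are shown at every visit, and that the endpoint has no p-value. All three are true. But visit-by-visit rates show losses only in aggregate and do not identify who held the response throughout, and the endpoint's label claims more than a Week 96 snapshot.

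Some stronger inferences are tempting but not supported:

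- **That PBO S48 is the trial's only evidence on the durability of spontaneous seroconversion.** SAP 7.5.2.5 and 7.5.8 report off-treatment seroconversion for the Post-Year 1 Efficacy Cohort, which separates placebo children who only ever received blinded placebo (PBO BL) from those given open-label ETV. PBO BL in 7.5.2.5 is selected on end-of-dosing status, but it is free of open-label ETV.
- **That ETV losses are repaired by a second course.** Protocol 5.3 uses the same drug and dosing table in the blinded and open-label phases.
- **That both maintained rates are certainly inflated.** This needs re-seroconversion, for which the documents give no rate.

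**Conclusion.** The point holds as a gap in definition. A Week 48 seroconverter who reverts and is seroconverted again at Week 96 is scored as maintained. On the likelier reading of SAP 7.5.4, a placebo child's success on ETV is credited to placebo.

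One such child moves the PBO S48 rate by roughly 17 to 31 points, assuming 60 placebo children and 5.3% to 10% seroconversion. Whether any such child will exist cannot be derived from the documents; with no re-seroconversion the maintained rate is undistorted. The mixing of on-ETV HBV DNA and ALT into PBO S48 needs only a placebo reverter with post-switch results.

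No type I error is at stake, because the endpoint is descriptive and outside the sequential tests. The change is worth making because the data are already collected and the label misdescribes what is computed.

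**What to change.** In SAP 7.5.4:

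1. Define maintained as seroconverted at Week 48 and at Week 96, with no observed HBeAg reversion at any on-treatment visit in between. Count any reversion as not maintained, whether or not open-label ETV followed. Base reversion on an observed HBeAg-positive result, because SAP 8.8 imputes indeterminate HBeAg as positive and one equivocal sample should not fail a child.
2. For PBO S48, cut all endpoints at the first open-label ETV dose, a date already derived in SAP 8.9, and show post-switch visits separately. List children switched without reversion separately rather than failing them. SAP Appendix 1 already has a deviation for open-label ETV after Week 48 seroconversion, but its label says no seroreversion while its definition requires it; settle that before reusing the code.
3. State whether the Week 48 limit on PBO also covers PBO S48.
4. Keep the Week 96 status rate as a supportive summary.

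The cost is SAP wording and one added derivation from existing serology and dose dates. Maintenance rates may come out slightly lower. No visit, sample or treatment rule changes.
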